### Sample Size Justification and Power Considerations

Since this is an early Phase I study, power considerations are limited but even so, we have excellent power to detect differences in specificity. With 14 subjects and an average of 30 nodes per subject, we expect 420 specimens on which to calculate and compare sensitivity and specificity. However, in calculating power, we must account for the clustering or correlation of lymph nodes within subject. Although we will use Durkalski's test to compare sensitivities and specificities, we estimated power by first determining the effective sample size (ESS), adjusting for the correlation of LNs within person, and then estimated power using McNemar's test on this ESS. We assumed an intra-class correlation of 0.005, yielding an effective sample size of 367 LNs. With an effective sample size of 367, a prevalence of 7.5%, a significance level of 0.05, and a 0.3 proportion of discordant pairs, we have greater than 95% power to detect a 0.1 difference in specificities, assuming the lower specificity is 0.7. Similarly, we have greater than 71% power to detect a 0.25 difference in sensitivity with the one-sided McNemar test. This assumes the proportion of discordant pairs is 0.3 and the lower sensitivity is 0.7.

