## 1. OBJECTIVES

### 1.1. Primary Objective

Determine the sensitivity and specificity of Zr-panitumumab for the detection of tumor-involved regional lymph nodes.

As defined by histological and/or pathological evaluation (gold standard), the total number of tumor-positive nodes will be determined for both Zr-panitumumab and F-FDG-PET imaging findings. The specificity and sensitivity of Zr-panitumumab will be calculated and compared to the specificity and sensitivity of F-FDG for metastatic lymph node identification. Additionally, we will determine the level of association between the Zr-panitumumab-PET results and F-FDG-PET results with the Phi coefficient.

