### **Primary objective**

**Determine the sensitivity and specificity of Zr-panitumumab for the detection of tumor-involved regional lymph nodes.**

Using the histological and/or pathological evaluation of the lymph node as the gold standard, we will calculate and compare the sensitivity and specificity of Zr-panitumumab and F-FDG PET/CT imaging findings. We will test the level of association of the Zr-panitumumab-PET results and the F-FDG-PET results with the Phi coefficient.

We will use the matched pair Durkalski's test (36), accounting for the cluster-correlation within subjects, for the sensitivity and specificity comparisons (primary and exploratory) using the clust.bin.pair package (37) in the R-statistical software (39). Significance for both primary and exploratory analyses will be assessed at the 0.05 level and to assess uncertainty, 95% confidence intervals will be provided for all estimates.

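### The stated power (>95% specificity, >71% sensitivity) is one-sided McNemar power, while the planned comparisons carry no direction and sit beside 95% confidence intervals; two-sided specificity power is about 91–93%

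*Combined protocol and SAP*

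**What the plan says.** The power paragraph in Section 12 (Sample Size Justification and Power Considerations) starts from 14 subjects with 30 nodes each and an intra-class correlation of 0.005, giving an effective sample size of 367. It takes a prevalence of 7.5%, "a significance level of 0.05, and a 0.3 proportion of discordant pairs". On that basis it states: "we have greater than 95% power to detect a 0.1 difference in specificities, assuming the lower specificity is 0.7". No side is given in that sentence. The next one reads: "Similarly, we have greater than 71% power to detect a 0.25 difference in sensitivity with the one-sided McNemar test", with discordance again 0.3 and the lower sensitivity 0.7. McNemar's test on the effective sample size stands in for Durkalski's test, which is the planned analysis. The paragraph opens with the claim that "we have excellent power to detect differences in specificity".

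The analysis text is neutral as to direction. Section 1.1 says the measures for the zirconium tracer "will be calculated and compared to the specificity and sensitivity of" FDG. Section 12, Primary objective, says "we will calculate and compare the sensitivity and specificity of" the two tracers, and adds: "Significance for both primary and exploratory analyses will be assessed at the 0.05 level and to assess uncertainty, 95% confidence intervals will be provided". The synopsis likewise sets 0.05 for all tests alongside 95% intervals. The term one-sided occurs only in the power paragraph. No section names a side for Durkalski's test or a hypothesised direction.

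**The concern.** Power should describe the test that will be run. Here the sensitivity figure is expressly one-sided and the specificity figure has no side. The analysis reads as a comparison in either direction, reported with intervals that correspond to a two-sided 0.05 test.

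Two things are at stake. First, if the test is two-sided, the plan overstates the chance of detecting the differences it names. Second, while the side is unstated it can be settled after the data are seen. If a one-sided 0.05 test were paired with ordinary 95% intervals, some trials would report a significant difference whose interval includes zero.

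**Working it through.** **Effective sample size (plan's inputs, Section 12).** Design effect = 1 + (30 − 1) × 0.005 = 1.145. Effective size = 420 / 1.145 = 366.8, which reproduces the stated 367.

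**Effective nodes per comparison.** Negative: 367 × 0.925 = 339.5, taken as 339. Positive: 367 × 0.075 = 27.5, taken as 27.

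**Discordant cells.** With discordance 0.3 and difference d, the cells are (0.3 + d)/2 and (0.3 − d)/2.
- Specificity, d = 0.1: 0.20 and 0.10.
- Sensitivity, d = 0.25: 0.275 and 0.025.

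**Exact McNemar power.** Let m be the number of discordant pairs, binomial(n, 0.3). Given m, the count in the favoured cell is binomial(m, p), with p = 0.20/0.30 = 0.667 for specificity and 0.275/0.30 = 0.917 for sensitivity. The test rejects when the upper tail of binomial(m, 0.5) is at most 0.05 (one-sided) or 0.025 (two-sided). Power is the rejection probability averaged over m.

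**Results, in %.**

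| McNemar version | Specificity, n = 339, one-sided | two-sided | Sensitivity, n = 27, one-sided | two-sided |
|---|---|---|---|---|
| Exact, enumerated | 95.3 | 91.2 | 71.4 | 58.9 |
| Continuity-corrected, enumerated | 95.3 | 91.1 | 71.4 | 58.9 |
| Mid-p, enumerated | 96.1 | 92.6 | 81.6 | 71.3 |
| Uncorrected, enumerated | 96.2 | 92.7 | 84.8 | 74.0 |
| Normal formula (Connor) | 96.0 | 92.3 | 79.3 | 67.8 |
| Normal formula (Miettinen) | 96.4 | 92.9 | 86.7 | 73.6 |
| Normal formula, alternative variance only | 96.2 | 92.8 | 84.6 | 76.0 |
| Normal formula, continuity-corrected | 95.0 | 90.7 | 66.3 | 52.7 |

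**Reproducing the plan's figures.** One-sided exact (or enumerated continuity-corrected) McNemar gives 95.3% and 71.4%, matching both claims under one method. At n = 28 the one-sided exact sensitivity figure would be 73.6%, so the plan appears to have used 27.

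**Hand check (Connor, specificity).** Power = Φ[(d√n − z√0.3) / √(0.3 − d²)].
- One-sided: (1.841 − 1.645 × 0.548) / 0.539 = 1.75, giving 96.0%.
- Two-sided: (1.841 − 1.960 × 0.548) / 0.539 = 1.43, giving 92.3%.

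**Could a two-sided test reach 95% for specificity?** Not on the plan's effective size. Counting all 367 effective nodes as negative gives 92.9–94.7% across the versions. In the enumerated versions, two-sided 95% needs 378 (uncorrected), 380 (mid-p) or 398 (exact and corrected) effective negative nodes, against 339. Some two-sided versions exceed 71% for sensitivity, but none gives both figures together.

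**How often the side decides the result.** Under the plan's own alternatives with the exact test, one-sided minus two-sided power is 95.3 − 91.2 = 4.1 points for specificity and 71.4 − 58.9 = 12.5 points for sensitivity. That is about 4 and 12 to 13 trials in 100.

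**The case against.** The strongest reply is that the basis is largely disclosed. The sensitivity sentence says one-sided, and its opening word *Similarly* ties it to the specificity sentence just before. Because one method reproduces both figures, it is fair to read one-sided as covering both. This stands as an account of how the power was calculated. It does not settle the side of Durkalski's test, which is what the result will be judged on.

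The stakes are also modest. This is a 14-subject pilot, the section itself says power considerations are limited, and two-sided specificity power stays above 90%, so calling it excellent is not refuted. That also stands.

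Three stronger readings are tempting and not supported:

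- A reader might infer that the stated figures are arithmetic errors. They are not; they reproduce from the stated inputs.
- A reader might infer that the plan commits to a two-sided test, so that the claim above 95% is simply false. No section states the side. Non-directional wording and 95% intervals point to two-sided, but that is an inference. Nor does any section expressly plan one-sided testing beside two-sided intervals.
- A reader might infer that any one-sided McNemar calculation meets both figures. The continuity-corrected normal formula gives 66.3% for sensitivity, below 71%.

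Nor can a power for Durkalski's test itself be taken from the documents. It depends on how the positive nodes are spread over subjects and on a correlation model, and neither is fully specified.

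**Conclusion.** The point holds as a mismatch between the power statement and the planned comparison. The two power figures stand together on a one-sided 0.05 basis, the specificity sentence does not say so, and the analysis as conventionally read is two-sided.

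On a two-sided basis, specificity power is about 91–93%. The chance of missing a true 0.1 difference is then about 7–9%, not under 5%. Sensitivity loses more: 71% to 59% with the exact test, up to 74% with the uncorrected enumerated test (76% with the most favourable normal formula), and 53% with the continuity-corrected normal formula.

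These sizes rest on the plan's own assumptions (intra-class correlation 0.005, prevalence 7.5%, discordance 0.3) and on McNemar's test standing in for Durkalski's. The omission of the side is certain; the loss of power is conditional on the test being two-sided. The point merits correction because these are the primary-objective comparisons, but it does not threaten the design.

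**What to change.** In Section 12 and in the synopsis's statistical considerations, state that Durkalski's test is two-sided at 0.05 for both sensitivity and specificity, consistent with the 95% intervals. Name the McNemar version behind the power figures and restate them on that basis. Suggested text:

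> Durkalski's test will be two-sided at the 0.05 level. On an effective sample size of 367 (about 339 negative and 27 positive nodes), two-sided exact McNemar power is about 91% for a 0.1 difference in specificity and about 59% for a 0.25 difference in sensitivity.

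If the sponsor intends a one-sided test, the plan should instead pre-specify the direction of both comparisons, label both power figures as one-sided, and report matching one-sided 95% (equivalently two-sided 90%) intervals for the differences.

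Any power quoted for Durkalski's test itself should come from the sponsor's own simulation, with the correlation model and the spread of positive nodes over subjects stated.

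The cost is one paragraph in Section 12 and one sentence in the synopsis. Enrolment and conduct do not change; on the two-sided basis the stated power becomes somewhat less favourable, mainly for sensitivity.

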## SCHEMA

[figure not shown]

Figure 1. Study overview.

**Study plan.** The study is an open label, single institution, pilot study to determine the distribution pattern of  $^{89}\text{Zr}$ -panitumumab and panitumumab-IRDye800 in subjects with head and neck squamous cell carcinoma (HNSCC) that undergo surgery with lymphadenectomy of curative intent. 30 mg of panitumumab-IRDye800 will be administered 1-5 days prior to surgery, intravenous (IV) over 15 min followed by an observation period of 30 min.  $^{89}\text{Zr}$ -panitumumab will be systemically injected at a dose of 1.0 mCi +/- 20%, and with a specific activity greater than 200 Ci/mmol at the time of injection. The injected mass dose is less than or equal to 1 mg (7 nmol); the subject will be monitored for 1 hour post-administration. If at any point two subjects in a cohort experience a DLT, then the study will stop and safety data will be reviewed. The medical monitor and safety review will occur independently.

There will be 7 subjects enrolled into each cohort (total of 14 subjects in the study) whereby, based on the preoperative work-up, including a physical exam and evaluation of the pre-existing imaging data, subjects will be assigned to the node negative or node positive group.

**Rationale for the two cohorts.** To ensure the inclusion of sufficient subjects with clinically positive lymph nodes, we created a cohort structure. Including both node-positive and node-negative subjects will ensure that we will have tumor-positive nodes when performing the data analysis. Moreover, by analyzing data from node-positive subjects it will become possible to assess if, in case large lymph node metastasis are present, the tracer(s) can still reach the node or if rerouting (a phenomenon known to happen in sentinel node mapping, i.e., drainage to a “false” sentinel node occurs because the “true” sentinel node cannot be reached). As shown in the study schema, all subjects regardless if enrolled in cohort 1 or 2, will undergo the same treatment, and upon data collection statistical analysis will be performed with the pooled data.

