## **10. MEASUREMENTS**

### **10.1 Primary Outcome Measure**

**The number (proportion) of lymph nodes determined to be tumor-positive by histological and/or pathological evaluation that were predicted to be tumor-positive by  $^{89}\text{Zr}$ -panitumumab labeling.**

We will compare the number and location of  $^{18}\text{F}$ -FDG-avid nodes within the regional lymphatics to the number and location of  $^{89}\text{Zr}$ -panitumumab-avid nodes in relation to the postoperative neck dissection histopathology (gold standard).

**Outcome Measure:** Preoperatively, the location and number of  $^{18}\text{F}$ -FDG-avid nodes as well as the number and location of  $^{89}\text{Zr}$ -panitumumab-avid nodes will be determined by 2 board-certified Nuclear Medicine physicians ([name] and [name]). Once all radioactive and fluorescent nodes are removed intraoperatively, standard of care will be

performed via completion neck dissection. The excised tissue specimens will be sent to pathology where the tumor status of the lymph nodes will be determined (histology serves as our gold standard). This will allow us to determine true and false positive and negative tumor values for Zr-panitumumab and F-FDG in identifying the tumor-loaded lymph nodes.

**Time Frame:** Final false positive and negative rate, sensitivity and specificity of sentinel node detection using Zr-panitumumab can be determined towards the completion of the trials (once all subjects have been included and all the data has been collected).

**Safety Issue:** No

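### The stated >71% power for sensitivity belongs to a one-sided McNemar test on 27 effective nodes, not to the planned Durkalski test in a sample where half the subjects are clinically node-negative.

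*Combined protocol and SAP*

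**What the plan says.** The primary outcome (Section 10.1) counts "lymph nodes determined to be tumor-positive by histological and/or pathological evaluation that were predicted to be tumor-positive" by the zirconium tracer, so the denominator for sensitivity is histologically positive nodes. The Schema sets the cohorts: "There will be 7 subjects enrolled into each cohort (total of 14 subjects in the study". Section 2.4 defines the node-negative cohort clinically, as cN0. Section 12 pools both cohorts.

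For the comparison with FDG, Section 12 (Primary objective) says: "We will use the matched pair Durkalski's test (36), accounting for the cluster-correlation within subjects". Significance is set at 0.05 with 95% confidence intervals, and no one-sided alternative is named there or in the Synopsis.

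The sample size text starts from node counts: "With 14 subjects and an average of 30 nodes per subject, we expect 420 specimens". It then allows for clustering: "We assumed an intra-class correlation of 0.005, yielding an effective sample size of 367 LNs". The remaining inputs are "a prevalence of 7.5%, a significance level of 0.05, and a 0.3 proportion of discordant pairs", and for sensitivity "This assumes the proportion of discordant pairs is 0.3 and the lower sensitivity is 0.7". The result is "we have greater than 71% power to detect a 0.25 difference in sensitivity with the one-sided McNemar test". The same paragraph says openly that McNemar's test on the effective sample size stands in for Durkalski's test.

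**The concern.** The power figure and the planned test use different units of information. McNemar's test on an effective sample size sees a number of nodes. Durkalski's test sums one net discordance per subject, so its power also depends on how many subjects have a positive node and how unequally those nodes are shared. Half the sample is chosen because no positive node is suspected, yet the power paragraph mentions neither the cohort split nor the expected number of node-positive subjects. It is also the only place where a one-sided sensitivity test appears.

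The comparison with FDG sensitivity is part of the primary objective. A reader who takes 71% at face value could give a non-significant result from about seven informative subjects more weight than it can bear.

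**Working it through.** **Inputs from the plan.** 14 subjects, 30 nodes each, intra-class correlation (ICC) 0.005, prevalence 7.5%, discordance 0.3, difference 0.25, level 0.05.

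**Reproducing the stated figure.**
- Effective sample size: 420 / (1 + 29 × 0.005) = 420 / 1.145 = 366.8, i.e. 367.
- Effective positive nodes: 367 × 0.075 = 27.5. Before deflation: 420 × 0.075 = 31.5.
- Discordant cells: (0.3 + 0.25)/2 = 0.275 and (0.3 − 0.25)/2 = 0.025.
- Exact McNemar power at n = 27: 71.4% one-sided, which matches the plan. The two-sided version gives 58.9%.

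**The planned test.** For each subject k with n_k > 0 positive nodes, let d_k = (b_k − c_k)/n_k, where b_k and c_k are the two discordant counts. The statistic is (Σd_k)² / Σd_k². By the Cauchy-Schwarz inequality it cannot exceed the number of subjects with d_k ≠ 0. Two-sided significance at 0.05 needs a value above 3.84, so at least 4 such subjects. With 3 or fewer it is impossible.

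**Simulated power of the planned test.** The discordant cells are as above, with Dirichlet-multinomial correlation within subject and critical values 1.645 (one-sided) and 1.96 (two-sided). The number of contributing subjects, the node spread and any ICC other than 0.005 are assumptions, because the plan gives none.

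| Contributing subjects | Positive nodes and spread | ICC | One-sided | Two-sided |
|---|---|---|---|---|
| 14 | 27, even | 0.005 | 83% | 67% |
| 14 | 31, even | 0.005 | 87% | 75% |
| 8 | 27, even | 0.005 | 79% | 57% |
| 7 | 27, even | 0.005 | 78% | 51% |
| 7 | 31, even | 0.005 | 82% | 57% |
| 7 | 31, as 12, 7, 4, 3, 2, 2, 1 | 0.005 | 68% | 30% |
| 7 | 27, even | 0.1 | 70% | 41% |
| 7 | 31, as 12, 7, 4, 3, 2, 2, 1 | 0.1 | 61% | 24% |
| 5 | 27, even | 0.005 | 70% | 26% |
| 4 | 27, even | 0.005 | 60% | 5% |
| 3 | 27, even | 0.005 | 29% | 0% |

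**Ranges.** These cover 27 to 32 positive nodes.
- 7 to 9 subjects, correlation near zero, even spread: about 77-86% one-sided and 51-69% two-sided.
- 7 to 9 subjects, correlation near zero, uneven spread with at least one positive node in every subject: about 64-75% and 27-48%.
- 7 subjects, ICC 0.1, even or uneven spread: about 56-75% and 21-47%.

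**The case against.** The plan can be defended on several points, and most of them stand.

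- **Clustering was not ignored.** A reader might infer that the nodes were simply treated as independent. The plan applied a design effect of 1.145 and disclosed that McNemar's test was an approximation. What can be questioned is the unsourced ICC and the silence on how positive nodes are distributed.
- **The figure is not shown to be inflated on its own terms.** A reader might infer that confining positive nodes to seven subjects takes power below 71%. With a one-sided test, ICC 0.005 and an even spread it does not: power is 78% with 27 nodes and 82% with 31. Exact McNemar is itself conservative. The shortfall needs a two-sided test, an uneven spread, a higher ICC, or about five or fewer contributing subjects.
- **cN0 is a clinical label.** A reader might infer that the cN0 cohort adds nothing to sensitivity. The Background says microscopic disease is found in many clinically negative necks, and Section 2.4 counts isolated tumor cells and micrometastases as positive. Some cN0 subjects may therefore contribute. With 10 contributing subjects, 31 nodes evenly spread and ICC 0.005, power is 85% one-sided and 69% two-sided.
- **The test is not left undefined for subjects without positive nodes.** Sensitivity is calculated among positive nodes, so leaving those subjects out follows from the definition. Saying so would help, but it is a detail.
- **This is a pilot.** Section 12 calls its power considerations limited and claims excellent power only for specificity.

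None of this makes 71% the power of the test that will be run.

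**Conclusion.** The point holds as a mismatch between a stated figure and the planned analysis. The figure is arithmetically right for one-sided exact McNemar on 27 effective nodes. It does not describe Durkalski's test at the 0.05 level in a sample with 7 cN0 and 7 cN+ subjects.

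The size of the mismatch depends mainly on sidedness and node spread. In the 7-to-9-subject cases above, one-sided power lies on either side of 71%, while two-sided power stays below it throughout. A two-sided test would pass 71% only in more favourable settings, such as 31 nodes spread evenly over all 14 subjects (75%). The documents do not support a general claim that power is overstated.

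The conclusion rests on three assumptions that the plan does not supply: the number of subjects with positive nodes, the spread of those nodes, and any ICC above 0.005. It is worth correcting because the comparison is part of the primary objective, but in a pilot of this size it is a moderate point.

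**What to change.** In Section 12:

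1. State whether the Durkalski test of sensitivity is one-sided or two-sided, and use the same choice in the analysis and power text.
2. Replace the single >71% figure with power simulated for that test, as a range over the number of subjects with positive nodes, the spread of those nodes and the ICC. Give the source or reasoning for each.
3. Say that subjects without a histologically positive node do not enter the sensitivity comparison, and report how many subjects do.
4. Report the sensitivity difference with a 95% interval that accounts for clustering by subject, and make that the main result for sensitivity.

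The cost is a short simulation and a few sentences. If the test is two-sided, the stated power will look less favourable. No extra patients are needed.

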## APPENDICES

### APPENDIX A: Participant Eligibility Checklist

A Participant Eligibility Checklist will be completed in its entirety for each subject prior to registration. The completed, signed, and dated checklist will be retained in the subject's study file and the study's Regulatory Binder.

The study coordinator, treating physician and an independent reviewer will verify that the participant's eligibility is accurate, complete, and legible in source records. A description of the eligibility verification process should be included in the EPIC or other Electronic Medical Record progress note.

Protocol Title:	Pilot study evaluating Panitumumab-Irdye800 and <math>^{89}\text{Zr}</math>-Panitumumab for dual-modality imaging for nodal staging in head and neck cancer
Protocol Number:	IRB-41878 / OnCore# ENT0066
Principal Investigator:	[name], MD

